10.3.1 Analysis of Mean Changes for Laboratory Tests

The following summaries of laboratory data will be included in the output: mean change from baseline to each double-blind visit value and to the minimum, maximum and final double-blind value for each continuous hematology, chemistry and urinalysis variable, mean change from final double-blind value to final post-treatment value presented for each continuous hematology, chemistry and urinalysis variable, shift tables, and potentially clinically significant laboratory values.

10.3.2 Shifts Between Normal and Abnormal for Laboratory Tests

Laboratory observations will be categorized as normal, low, or high relative to the reference (normal) range associated with the laboratory that performed the assay. For each hematology, chemistry and urinalysis variable with a reference range, shift tables will be prepared for shifts from baseline to lowest, highest and final value during the entire study for each treatment group and overall subjects. No comparisons of treatment groups will be performed. Shift tables will also be prepared by geographical region. The tables will present:

- The numbers and percentages of subjects with low or normal observations at baseline who have a high observation at any post-baseline visit
- The numbers and percentages of subjects with normal or high observations at baseline who have a low observation at any post-baseline visit
- The numbers and percentages of subjects with low or normal observations at baseline who have a high observation at the final visit
- The numbers and percentages of subjects with normal or high observations at baseline who have a low observation at the final visit

10.3.3 Potentially Clinically Significant Laboratory Values

Criteria for potentially clinically significant (PCS) values have been predefined for selected laboratory variables as outlined in [Appendix A](#). For each variable, a summary of the number and percentage of subjects in each treatment group who have at least one double-blind observation that meets the PCS criteria and is more extreme than their baseline value will be provided. A listing will also be prepared that will include, for each variable, all observations for each subject that met the PCS criteria for that variable at any time during the study.

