8.1.2.3 Analysis of Laboratory Tests

Analyses will be performed on the Stand-Alone data set for laboratory tests. Change from Baseline to each visit value and to the minimum, maximum, and final value will be presented for each continuous hematology, chemistry, and urinalysis parameter.

Treatment differences between treatment group in change from Baseline to minimum, maximum, and final clinical laboratory evaluation will be analyzed using a one-way ANOVA with treatment group as the main effect.

For each treatment group, shift tables will be generated showing the number and percentage of subjects with low, normal, high, and missing values at Baseline and final observation based on the reference ranges provided by each laboratory. Details will be specified in the SAP.

The number and percentage of subjects in each treatment group who have values meeting predefined criteria for PCS ([Appendix D](#)) at any time after the first dose of study drug and no more than 20 weeks after the last dose of study drug will be summarized separately for hematology and chemistry variables. No comparisons between treatment groups will be performed for PCS analysis.

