8.1.2.4 Analysis of Vital Signs and Weight

Vital sign variables for this study will be pulse rate, systolic blood pressure, diastolic blood pressure, body temperature, weight, and body mass index (BMI). Pulse rate and blood pressure will be measured in both supine and standing positions; orthostatic change (from supine to standing) will also be measured.

Change from Baseline to each visit value and to the minimum, maximum, and final value will be presented for each vital sign and weight variable and analyzed using a one-way ANOVA with treatment group as the main effect. The number and percentage of subjects in each treatment group who have values meeting predefined criteria for PCS (definitions will be provided in the SAP) at any time after the first dose of study drug and no more

than 20 weeks after the last dose of study drug will be summarized. No comparisons between treatment groups will be conducted.

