8.1.2.5 Analysis of ECG Variables

ECG variables for this study will be heart rate, PR, QRS, QT, and QTcF intervals. Change from Baseline to final value will be presented for each ECG parameter and analyzed using a one-way ANOVA with treatment group as the main effect. The number and percentage of subjects in each treatment group who have values meeting predefined criteria for PCS at any time after the first dose of study drug will be summarized.

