10.0 Safety Analysis

10.1 General Considerations

Comparisons between treatment groups (Studies M15-562/M15-563) of interest will not be performed.

All other safety assessments that are taken no more than 45 days after the last dose of study drug will be included in the safety evaluation of the Treatment Period, and all safety assessments that are taken more than 45 days but not more than 20 weeks after the last dose of study drug will be included in the safety evaluation for the Post-treatment Follow-up Visit.

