10.4.2 Potentially Clinically Significant Vital Sign and Weight Values

Criteria for potentially clinically significant values have been predefined for selected vital sign and weight variables as outlined in Appendix. For each variable, a summary of the number and percentage of subjects in each treatment group who have at least one double blind observation that meets the PCS criteria and is more extreme than their baseline value will be provided. A listing will also be prepared that will include, for each variable, all observations for each subject that met the PCS criteria for that variable at any time during the study.

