10.5.2 Potentially Clinically Significant ECG Values

Criteria for potentially clinically significant values have been predefined for selected ECG variables as outlined in [Appendix C](#). For each variable, a summary of the number and percentage of subjects in each treatment group who have at least one double-blind observation that meets the PCS criteria and is more extreme than their baseline value will be provided. Listings will also be prepared to include all observations for each variable for each subject that met the PCS criteria for that variable at any time during the study. No comparisons of treatment groups will be performed.

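### The SAP counts potentially clinically significant values only while on treatment, where the protocol counts them to 20 weeks after the last dose (ECG: no end date), and does not declare the change

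*SAP*

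**What the plan says.** The protocol sets the PCS window separately for each type of assessment.

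- Laboratory tests (Protocol 8.1.2.3): a value counts "at any time after the first dose of study drug and no more than 20 weeks after the last dose of study drug".
- Vital signs and weight (Protocol 8.1.2.4): qualifying values arising no later "than 20 weeks after the last dose of study drug will be summarized".
- ECG (Protocol 8.1.2.5): values meeting "criteria for PCS at any time after the first dose of study drug will be summarized", with no end date.

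The SAP uses one restriction for all three.

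- Laboratory tests (SAP 10.3.3): the subject needs "at least one double-blind observation that meets the PCS criteria and is more extreme than their baseline value".
- Vital signs and weight (SAP 10.4.2): a "double blind observation that meets the PCS criteria and is more extreme than their baseline value".
- ECG (SAP 10.5.2): a "double-blind observation that meets the PCS criteria and is more extreme than their baseline value".

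SAP 10.1 places assessments "taken no more than 45 days after the last dose of study drug" in the Treatment Period and assigns those after 45 days, up to 20 weeks, to the post-treatment follow-up evaluation. Treatment-emergent adverse events run to 20 weeks in both documents (Protocol 8.1.2; SAP 10.2).

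**The concern.** A programmer following the SAP must decide what *double-blind* means in M15-563. SAP 4.2 uses the term for the parent study, M15-562. The PCS analyses use the Stand-Alone data set, which contains M15-563 data only. If the term means on treatment, a PCS value seen 10 weeks after the last dose counts under the protocol and not under the SAP. An adverse event reported for that same laboratory value would still be in the treatment-emergent table, so two safety tables in one report would rest on different windows. Long-term safety is a primary objective, and nothing in the SAP presents this as a change from the protocol.

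**Working it through.** **Step 1: what *double-blind* must mean.** SAP 10.3.1 (laboratory) and 10.5.1 (ECG) each plan a mean change from the final double-blind value to the final post-treatment value. The two periods are therefore distinct, and the only boundary the SAP gives is the 45-day rule in 10.1. This is an inference, since no definition is stated.

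**Step 2: where values after day 45 are reported.**

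| Assessment | Protocol PCS window | SAP PCS count | Where later values still appear |
|---|---|---|---|
| Laboratory | To 20 weeks (8.1.2.3) | On treatment (10.3.3) | PCS listing; whole-study shift tables (10.3.2); post-treatment mean change (10.3.1) |
| Vital signs, weight | To 20 weeks (8.1.2.4) | On treatment (10.4.2) | PCS listing |
| ECG | After first dose, no end (8.1.2.5) | On treatment (10.5.2) | PCS listing; post-treatment mean change (10.5.1) |

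No post-treatment PCS count is planned in any row. The shift tables use laboratory reference ranges, not PCS thresholds.

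**Step 3: the period removed (laboratory, vital signs, weight).** 20 weeks = 140 days. 140 − 45 = 95 days, and 95/140 = 68% of the post-dose window.

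**Step 4: the protocol's own figure.** Protocol 6.1.4 equates 20 weeks with about 5 half-lives. Protocol 3.0 gives a half-life of 27 to 37 days from the single-dose study. 140/27 = 5.2, 140/28 = 5.0 and 140/37 = 3.8. The stated figure is reproduced only at the short end of the range.

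**Step 5: drug remaining.** With first-order decline, the fraction left at day d is 2^(−d/t½).

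| Day after last dose | t½ = 27 days | t½ = 37 days |
|---|---|---|
| 45 | 2^(−45/27) = 31.5% | 2^(−45/37) = 43.0% |
| 140 | 2^(−140/27) = 2.7% | 2^(−140/37) = 7.3% |

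The level falls to 10% at t½ × log2(10), which is day 90 (t½ 27) to day 123 (t½ 37).

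**Step 6: which samples fall where.** The one visit scheduled for every subject in the removed period is the follow-up visit at about 20 weeks, when 2.7–7.3% remains. The 31–43% figure describes a sample taken just after day 45. Only a late discontinuation assessment, a repeat or an unscheduled test would fall there.

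**The case against.** The strongest reply is that little is lost. Protocol 8.1.2 itself splits safety assessments at 45 days, so the SAP is following a protocol rule. Protocol 5.3.1.1.10 requires each PCS laboratory value either to be reported as an adverse event or to have the reason for not doing so documented, so an important one reaches the adverse event tables. The PCS tables are descriptive, with no comparison between groups.

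Much of this stands as a limit on size. It does not remove the discrepancy. The 45-day split is the protocol's general rule, while 8.1.2.3 and 8.1.2.4 give a specific PCS window that runs past it. The adverse event route depends on investigator judgement and, as written, covers laboratory values and not vital signs or ECG. A listing gives no count or percentage by group.

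Three stronger readings are tempting, and the documents do not support them.

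- **A reader might infer that follow-up abnormalities are lost while substantial drug is present.** At the scheduled visit only about 3–7% remains.
- **A reader might infer that the lost values appear only in a listing.** That is so for vital signs and weight. Laboratory values also enter the shift tables and the post-treatment mean change, and ECG values enter the latter.
- **A reader might infer that a large share of all post-baseline tests is lost.** Discontinuation samples are due as soon as possible (Protocol 5.4.1), and those taken within 45 days of the last dose still count. For a subject stopping after Week 52, with laboratory tests at Weeks 12, 24 and 52, a follow-up test would be 1 of 4, or 1 of 5 with a discontinuation test. The share falls with longer treatment. These counts are approximate because the columns of Appendix C are hard to align in the text available.

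**Conclusion.** The mismatch is real: on its natural reading, the SAP undercounts PCS values against the protocol's own rule, across laboratory tests, vital signs, weight and ECG. The effect is modest, and this is a minor correction. It removes 95 of 140 post-dose days from the counts and percentages, but the sample expected in that period is the week-20 one, and the values stay traceable in the listings.

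The conclusion rests on reading *double-blind* as on treatment. The drug-level figures also assume first-order decline and that the single-dose half-life range carries over to repeated dosing. The number of PCS values affected cannot be estimated from the documents.

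**What to change.** In SAP 10.3.3, 10.4.2 and 10.5.2, replace *double-blind observation* with: observation after the first M15-563 dose through 20 weeks after the last dose, including the follow-up visit within its ±4-day window. For ECG, use any time after the first dose, as in the protocol. The visit allowance matters because a strict 140-day limit would drop follow-up visits on days 141–144.

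Alternatively, keep the on-treatment count, define the period, add a separate post-treatment PCS summary, and declare the change from the protocol.

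Under either option, compare vital signs only with a baseline taken in the same position. Protocol 5.3.1.1.5 measures ordinary vital signs sitting, whereas SAP 10.4 analyses supine and standing values.

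The cost is a wording change, a wider data filter and a position-matching rule. PCS counts may rise slightly and will include some values taken when little drug remains.

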10.4 Analysis of Vital Signs and Weight

Vital sign and weight data analyses will be performed on Stand-Alone data set. Vital sign variables include: diastolic blood pressure, systolic blood pressure and pulse rate at

supine and standing positions, orthostatic diastolic blood pressure, orthostatic systolic blood pressure, orthostatic pulse rate, and body temperature. The calculations of orthostatic vital sign values are:

- Orthostatic SBP (mmHg) = Standing SBP – Supine SBP
- Orthostatic DBP (mmHg) = Standing DBP – Supine DBP
- Orthostatic Pulse Rate (bpm) = Standing Pulse Rate – Supine Pulse Rate.

Weight variables include weight and BMI.

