5.0 Investigational Plan

5.1 Overall Study Design and Plan: Description

Overview

Study M15-563 is a long-term extension of Study M15-562, a Phase 2, randomized, multiple-dose, multicenter study in subjects with PSP. Subjects who completed the 52-week Treatment Period in Study M15-562 and meet all entry criteria will be eligible for enrollment into Study M15-563. Study M15-562 was designed to randomize 378 subjects to meet scientific and regulatory objectives without enrolling an undue number of subjects in alignment with ethical considerations. Therefore, the number of subjects who will participate in Study M15-563 will be up to the number of subjects enrolled in Study M15-562 (the actual number of subjects who enroll in Study M15-563 will depend on the number of subjects from Study M15-562 who are eligible and consent to rollover). The study will be conducted at approximately 60 multinational sites.

Study M15-563 will consist of a treatment period of up to 5 years and a post-treatment follow-up visit approximately 20 weeks after the last dose of study drug (including subjects who prematurely discontinue treatment). All subjects will receive ABBV-8E12 as follows: 1) subjects who received placebo in Study M15-562 will be randomized, in a

1:1 ratio, to 1 of 2 ABBV-8E12 doses (2000 or 4000 mg); and 2) subjects who received ABBV-8E12 2000 or 4000 mg in Study M15-562 will continue on the same dose. Refer to Section 5.5.3 for detailed information on randomization. Investigators and subjects will remain blinded to the treatment assignments in Study M15-562 and will be blinded to the dose level of ABBV-8E12 in Study M15-563.

Subjects from Study M15-562 will complete baseline procedures and receive the first infusion of study drug on Day 1 of Study M15-563. For subjects who do not have interruptions in study drug administration between Study M15-562 and Study M15-563 (i.e., the duration between the last dose of study drug in Study M15-562 and the first dose of study drug in Study M15-563 is no more than 45 days), procedures that were performed at the Week 52 Visit in Study M15-562 do not need to be repeated for the Day 1 Visit in Study M15-563. Week 52 procedures from Study M15-562 cannot be used to satisfy the Day 1 requirements for Study M15-563 if more than 45 days (but less than 8 weeks) have elapsed since the subject's last dose of study drug in Study M15-562; in that case, Day 1 activities for Study M15-563 must be performed.

[figure not shown]

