8.0 Statistical Methods and Determination of Sample Size

The data analysis will be grouped by assigned treatment sequences/group in Studies M15-562/M15-563: 2000/2000 mg, 4000/4000 mg, placebo/2000 mg, and placebo/4000 mg. If the treatment effect between each ABBV-8E12 dose and placebo is statistically significant at Week 52 in Study M15-562, the 2000/2000 mg and 4000/4000 mg groups could be combined as the early-start ABBV-8E12 treatment group, and the placebo/2000 mg and placebo/4000 mg groups could be combined as the delayed-start group for the delayed-start analysis. Details of the analyses will be specified in the statistical analysis plan (SAP).

Data Sets for Efficacy Analyses

Two data sets will be used for the efficacy analysis: an intent-to-treat (ITT) data set and a delayed-start data set.

ITT Data Set: The Study M15-563 ITT data set consists of all subjects who received any dose of study drug in Study M15-563. This is the primary efficacy analysis set for this

study. All efficacy analyses for Study M15-563 alone will be conducted on the ITT set unless otherwise specified.

Delayed-Start Data Set: The delayed start analysis data set includes efficacy data from both Studies M15-562 and M15-563. All subjects from Study M15-562 ITT data set will be included, regardless if they enroll in Study M15-563 or not. Subjects who complete Study M15-562 and rollover to Study M15-563 but have a gap of more than 8 weeks between study drug infusions before enrolling into Study M15-563 will be excluded from this analysis set.

Data Sets for Safety Analyses

The safety data sets will consist of all subjects who received any dose of study drug in Study M15-563. For the safety analyses, the actual treatment received will be used instead of the treatment assignment at the time of randomization. There are 2 safety datasets: a Stand-Alone safety data set and a cumulative safety data set as described below.

Stand-Alone Data Set: The stand-alone data set is the primary data set for the safety analysis, and will contain data from Study M15-563 only, regardless of the treatment received in Study M15-562. Baseline will be the last observation on or before the first dose of ABBV-8E12 in Study M15-563. If no Baseline is recorded in Study M15-563, the last value in Study M15-562 will be used as the Baseline.

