4.2 Study Design

This study is a long-term extension of the Phase 2, double-blind study, Study M15-562. Subjects who completed the 52-week Treatment Period in Study M15-562 will be eligible for enrollment into Study M15-563. All subjects in Study M15-563 will receive ABBV-8E12 as follows: 1) subjects who received placebo in Study M15-562 will be randomized, in a 1:1 ratio, to 1 of 2 ABBV-8E12 doses (2000 or 4000 mg); and 2) subjects who received ABBV-8E12 2000 or 4000 mg in Study M15-562 will continue on the same dose. Investigators and subjects will remain blinded to the treatment assignments in Study M15-562 after database lock and will be blinded to the dose level of ABBV-8E12 in Study M15-563.

Subjects who enroll in Study M15-563 from Study M15-562 will complete baseline procedures and receive their first infusion of study drug on Day 1 of Study M15-563. For subjects who do not have interruptions in study drug administration between Study M15-562 and Study M15-563, i.e., the duration between the last dose of study drug

[figure not shown]
infusion in Study M15-562 and the first dose of study drug in Study M15-563 is no more than 45 days, assessments that were performed at the Week 52 Visit in Study M15-562 will be used for the Day 1 Visit assessments in Study M15-563. If a subject enrolled in Study M15-563 is more than 45 days but less than 8 weeks since the subject's last dose of study drug in Study M15-562; in that case, Day 1 activities for Study M15-563 must be performed.

Subjects will receive 3 infusions of study drug during the first 4 weeks of Study M15-563, the first on Day 1, the second on Day 15 (subjects who received placebo in Study M15-562 will receive ABBV-8E12 on Day 15 of Study M15-563, and subjects who received ABBV-8E12 in Study M15-562 will receive placebo on Day 15 of Study M15-563 to maintain the blind in Study M15-562), and the third on Day 29. After Day 29, subjects will receive study drug infusions every 28 days and will continue to receive ABBV-8E12 until one of the discontinuation criteria is met, until the study is discontinued by the Sponsor, or until the study reaches completion. Subjects will return to the site approximately 20 weeks after their last dose for a post-treatment Follow-up Visit.

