5.0 Analysis Populations

5.1 Analysis Data Sets

Data Sets for Efficacy Analyses

Two data sets will be created for the efficacy analysis: an intent-to-treat (ITT) data set and a delayed-start data set.

ITT Data Set: the ITT data set consists of all subjects who received any dose of study drug in Study M15-563. All efficacy analyses will be conducted on the ITT data set using data from Study M15-563 alone unless otherwise specified.

Delayed-Start Data Set: The Delayed-Start data set includes all subjects from the Study M15-562 ITT data set who received placebo or ABBV-8E12 in Study M15-562 regardless of whether they enroll in Study M15-563 or not. For the Delayed-Start analysis, efficacy data for PSPRS total score from both Study M15-562 and Study M15-563 studies will be included.

Data Sets for Safety Analyses

The safety data set will consist of all subjects who received any dose of study drug infusion in Study M15-563. For safety analyses, the actual treatment received will be used instead of the treatment assignment at enrollment. There are two safety data sets: a Stand-Alone data set and a Cumulative data set.

Stand-Alone Data Set: The Stand-Alone data set is the primary data set for safety analyses, and will contain data from Study M15-563 only, regardless of the treatment received in Study M15-562. Baseline for the Stand-Alone data set will be the last observation on or before the first dose of ABBV-8E12 in Study M15-563. If no Baseline is recorded in Study M15-563, the last value in Study M15-562 will be used as the Baseline.

Cumulative Data Set: The Cumulative data set will consist of data from both Study M15-562 and Study M15-563. It is the secondary data set for safety analyses. For subjects who were in the placebo group in Study M15-562, their safety data from Study M15-562 will not be included in the Cumulative data set but their safety data from Study M15-563 will be included. For subjects who were in the placebo group in Study M15-562, Baseline will be the last observation prior to the first dose of study drug in Study M15-563. For subjects who were in ABBV-8E12 treatment groups in Study M15-562, Baseline for the Cumulative data set will be their Baseline in Study M15-562.

Data Sets for Biomarker Analyses

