10.4.1 Analysis of Mean Changes for Vital Sign and Weight

Diastolic blood pressure, systolic blood pressure and pulse will be analyzed separately for each position of measurement. Analyses of mean change from baseline to each double blinded visit value and to the minimum, maximum and final double-blind value will be presented for each vital sign and weight variable. Analysis of orthostatic SBP, DBP and pulse rate will be conducted similarly.

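### The SAP defines blood pressure and pulse as supine, standing and orthostatic, but all 52 visits in Years 2 to 5 schedule seated readings only, with no seated variable and no scheduled seated baseline

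*SAP*

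**What the plan says.** **Variables.** SAP 10.4 lists blood pressure and pulse at "supine and standing positions, orthostatic diastolic blood pressure, orthostatic systolic blood pressure, orthostatic pulse rate, and body temperature". Protocol 8.1.2.4 begins without a posture ("Vital sign variables for this study will be pulse rate, systolic blood pressure, diastolic blood pressure") and then fixes one: "Pulse rate and blood pressure will be measured in both supine and standing positions". SAP 10.4.1 says that blood pressure and pulse will be "analyzed separately for each position of measurement". None of these sections mentions sitting.

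**Schedule.** The protocol defines two procedures. Orthostatic vital signs (5.3.1.1.4) are supine and then standing. Vital signs (5.3.1.1.5) are taken after at least 5 minutes seated. Protocol Appendix C and SAP Table 2 mark the orthostatic procedure at every Year 1 dosing visit, Day 1 to Week 52. In Years 2 to 5 the orthostatic row is absent and only the seated procedure is scheduled.

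**Baseline.** For the Stand-Alone data set, "Baseline will be the last observation on or before the first dose of ABBV-8E12 in Study M15-563" (Protocol 8.0). SAP 5.1 repeats this rule, and both documents add a fallback: "If no Baseline is recorded in Study M15-563, the last value in Study M15-562 will be used as the Baseline". Where the gap between the last M15-562 dose and the first M15-563 dose is no more than 45 days, Protocol 5.1 says that "procedures that were performed at the Week 52 Visit in Study M15-562 do not need to be repeated for the Day 1 Visit", and SAP 4.2 that "assessments that were performed at the Week 52 Visit in Study M15-562 will be used for the Day 1 Visit assessments". No rule mentions position. Protocol 5.3.1.1.4 makes the pre-dose orthostatic set on Day 1 the baseline for clinical assessment.

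**PCS criteria.** SAP Appendix B gives a low and a high criterion for each of SBP, DBP and pulse. All six combine a threshold with a change from baseline, and none states a posture.

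**The concern.** The variable list and the data collection part company after Week 52, and a programmer working from the SAP has no rule for what follows.

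1. **Follow the named list.** Blood pressure and pulse from Week 56 onward are left out. The by-visit, minimum, maximum, final and PCS results then describe Year 1, even for a subject who completes Year 5.
2. **Admit seated values as a position of their own.** They then need a seated baseline, and M15-563 schedules none.

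A programmer who matches on parameter name alone could also compare a seated value with a supine or standing baseline, so that a change of posture would be counted as a change over time.

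The outputs affected are the mean-change tables (SAP 10.4.1), the PCS summary and PCS listing (SAP 10.4.2), and the PCS summary in Protocol 8.1.2.4, which runs to 20 weeks after the last dose. Long-term safety is a primary objective and treatment lasts up to 5 years, so the later years are what this study adds to its 52-week parent.

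**Working it through.** **Step 1: reproduce the schedule.** Inputs from Protocol Appendix C and SAP Table 2: visits on Days 1, 15 and 29, then every 28 days to Day 1821 (Week 260, no dose). This gives 67 visits and 67 − 1 = 66 doses, which agrees with the plan's own label of Dose 66 as the final dose.

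**Step 2: split by procedure.** Discontinuation and follow-up columns are not counted.

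| Period | Visits | Doses | Blood pressure and pulse procedure |
|---|---|---|---|
| Year 1 (Day 1 to Week 52) | 15 | 1–15 | supine and standing |
| Years 2–5 (Weeks 56 to 260) | 13 × 4 = 52 | 16–66 (51 doses) | seated |

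- Share of visits: 52/67 = 77.6%.
- Share of doses: 51/66 = 77.3%.
- Gap for a Week 260 completer: Day 1821 − Day 365 = 1456 days = 208 weeks between the last scheduled supine and standing reading and the last treatment-period visit.
- Day 1821 is 1821 − 1793 = 28 days after the last dose, inside the 45-day treatment-period window, so the Week 260 reading counts as on-treatment.

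**Step 3: allow for attrition.** The documents give no retention figure. As an assumption, let a subject attend the visit at week *w* with probability *r*^(*w*/52), where *r* is yearly retention. Summing over the visits in Step 2 gives the expected number per enrolled subject; the late share is Years 2–5 divided by the total.

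| Assumed *r* | Year 1 visits | Years 2–5 visits | Late share |
|---|---|---|---|
| 0.9 | 14.28 | 38.03 | 72.7% |
| 0.8 | 13.54 | 27.28 | 66.8% |
| 0.7 | 12.77 | 19.12 | 60.0% |
| 0.6 | 11.96 | 13.03 | 52.1% |
| 0.5 | 11.10 | 8.56 | 43.5% |

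The late share equals one half at *r* = 0.574.

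**Step 4: can any rule supply a seated baseline?**

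- *M15-563 Day 1:* the scheduled set is orthostatic, so no.
- *M15-562 fallback:* it applies only when M15-563 has no baseline. Neither document says whether a supine Day 1 value counts as a recorded baseline for a seated reading. Even if the rule is applied by position, it works only if M15-562 took seated readings.
- *Week 52 carry-over:* it depends on that same condition, which these documents do not show.

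**Step 5: is the missing row an extraction fault?** Unlikely. Both documents show the same pattern in all four later years, and the Year 1 footnote on supine and standing readings is also absent from the Year 2 to 5 footnotes.

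**The case against.** The best counter-argument is that the plan, read as a whole, already admits seated values. SAP 10.1 puts every safety assessment taken within 45 days of the last dose into the treatment-period evaluation. SAP 4.6 lists vital signs with no posture. SAP 10.4 introduces its list as what the variables include, which need not be exhaustive, and SAP 10.4.1 provides for analysis by position. On this view a same-position baseline is the natural reading, the M15-562 fallback fills the gap, and the remedy is a drafting clarification.

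Part of this stands. Including seated values is a reasonable reading, and the baseline difficulty does depend on what M15-562 collected. But the 45-day rule is a time window: it names no seated variable and no baseline. Analysis by position is also what creates the need for a seated baseline, so this reading exchanges the first problem for the second.

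Other limits also stand. The 78% and 77% figures are no-attrition ceilings in a disease the protocol calls uniformly fatal, and the retention table rests on an assumed model. The SAP makes no treatment comparisons, so these are descriptive tables. Vital-sign changes that qualify as adverse events are still captured there, and the DMC reviews vital signs separately. Temperature, weight and BMI are unaffected. These points bound the consequence; they do not supply the missing variable or baseline.

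**Conclusion.** The concern holds: SAP 10.4 is wrong as written for Years 2 to 5. That the seated readings have no named variable, and no scheduled M15-563 baseline, follows directly from the two documents and needs no assumption.

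The mismatch covers 52 of 67 planned treatment-period visits with full attendance. Under the assumed constant retention, the share of attended visits is 73% at 90% a year and 44% at 50%, and it exceeds half while retention is above about 57% a year. These are shares of visits, not estimates of missed events. Whether some subjects have a usable seated baseline from M15-562 cannot be settled from these documents. The point should be corrected, because a literal reading confines blood pressure and pulse results to the first of up to five years.

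**What to change.** - In SAP 10.4 and Appendix B, add seated SBP, DBP and pulse as analysed variables.
- In SAP 5.1, state that the Stand-Alone baseline and its M15-562 fallback apply separately to each position.
- Where a subject has no seated baseline, summarise observed seated values by visit, and do not screen them against a supine or standing baseline.
- Label the supine, standing and orthostatic summaries, including final, minimum and maximum, as Year 1 only.
- Reconcile Protocol 8.1.2.4 with the schedule in Appendix C.

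The cost is SAP wording and a few extra tables on data already scheduled, with no new measurements. One limit remains: the change-based PCS criteria cannot be assessed on seated values for subjects without a seated baseline, and the tables should say so.
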